BUTLER HOSPITAL
INSTITUTIONAL REVIEW BOARD
PROTOCOL

1.) Project

Title of Project: Development of an Adjunctive Video-Based Suicide Prevention Intervention Immediately Following Psychiatric Hospitalization

Principal Investigator (PI): [name].

Other Investigator(s): [name]., [name]., [name]., [name].

2.) Description of Study

A. Specific Aims

- 1) **Phase 3:** We will conduct a pilot RCT (n=40) of hospitalized patients (including people enrolled in a partial hospital program) with a recent suicide attempt/plan who will receive treatment as usual (TAU) plus *LifePlans* vs TAU only. We will examine *LifePlans* feasibility and acceptability (video viewing, engagement, satisfaction, recruitment/retention), treatment differences (within relevant confidence intervals) on outcomes (e.g., suicide behaviors), and change on potential mechanisms.

B. Background

Suicide and attempted suicide are major public health issues in the U.S., accounting for almost 45,000 deaths in 2016, and over 1 million attempts each year. Although recent years have seen significant advances in our knowledge of efficacious treatments for many psychiatric disorders, the suicide rates in the U.S. have been increasing since 2000. Even with increased efforts in recent years, there still has been a relative paucity of research devoted to developing or testing innovative interventions directly targeting suicidal behavior to reach those most in need. Some treatments (e.g., cognitive behavior therapies) have been found to reduce rates of suicide attempts, but these interventions require substantial training and are lengthy and costly to administer. On the other hand, minimally intensive interventions (e.g., follow-up letters, postcards) have shown mixed results. More efficient and effective “middle ground” interventions developed to prevent suicidal behavior are clearly needed. We urgently need interventions based on evidence-based principles that decrease suicidal behavior and are feasible to deliver to large numbers of patients at times when their risk for suicide is high.

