We will ask participants to complete additional assessments reflecting the content of LifePlans. Participants will complete video completion surveys of the time that they spend watching the video and the particular sections watched. If they did not watch the videos, participants will answer questions on any barriers that prevented them from watching. To assess transportation/engagement, we use a modified version of the Transportation Scale⁹ (11 items) we previously developed that is appropriate for watching a video. Sample items include: "The [video about XX] affected me emotionally" or "I found my mind wandering while [watching the video about XX]." Items are rated from 1 "not at all" to 7 "very much." The total scale score is calculated by taking the average of all items. In addition, participants will complete a Video Acceptability Scale, which is adapted from a 7-item Likert-scale measure (1=not at all and 7=very much) designed for technology-assisted interventions by Ondersma et al.¹⁰ that assesses how participants feel about their experience: overall liking, interesting, ease of use, understandable, respectful, or annoying. To assess message understanding, we will use a Message Scale, which consists of questions designed to: 1) enhance the impact of the intervention; and 2) provide data to us about their reactions to the video. The questionnaire includes these questions: 1) What did you like about this video? What did you not like about this video?; 2) What was the main message that you got from watching this video?; 3) Does this video have any relevance to your life? What relevance does it have to your life?; and 4) What might you do differently as a result of watching this video? We will use qualitative data analysis techniques to analyze participants' responses.

Research Assessments – Open Trial and Pilot RCT (phases 2 and 3)		
	Purpose	Timepoints
Treatment Acceptability, Feasibility, Uptake, Transportation		
Credibility Expectancy Questionnaire	P	BL
Client Satisfaction Questionnaire	P,O	M1
Qualitative Interview	P	M1
Video Completion Surveys	P	W1, W2, W3, W4
Transportation Scale	P	M1*
Video Acceptability Scale	P	M1*
Message Scale	P	M1*
Psychiatric Symptoms and Functioning		
Columbia Suicide Severity Rating Scale	O**	BL, M1, M6
Modified Scale for Suicide Ideation-	O	BL, M1, M6
PROMIS-29	O	BL, M1, M6
PROMIS Depression Short Form***	O	W1, W2, W3, W4
Hospital chart review	I,O	BL, M6
Psychosis Screening Questionnaire	I	BL

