Mental Help Seeking Attitudes Scale	O	BL, M1, M6
Personal Suicide Stigma Questionnaire (self-blame subscale only)	O	BL, M1, M6
Potential Mechanisms (CLASP Targets)		
Multidimensional Scale of Perceived Social Support	Med	BL, M1, M6
Brief COPE	Med	BL, M1, M6
Valuing Questionnaire	Med	BL, M1, M6
Treatment Utilization		
Treatment History Interview		BL, M1, M6
Outpatient and Hospital Chart Review		BL, M1, M6
Note. Purpose: P=Pilot study target outcome; O=Outcome in large-scale RCT; I=Inclusion criteria; O**=Primary outcome in large-scale RCT; C=Characterize sample; Med=Potential mediator in a larger scale RCT. Timepoints: BL=baseline; W1, W2, W3, W4=Week 1, 2, 3, and 4 of the intervention. M1 and M6=Month 1 and 6. M1*=M1 during the pilot RCT, but weekly during the open trial.*** The PROMIS Depression Short Form was added for the pilot RCT.		

Suicidal Behaviors. The Columbia Suicide Severity Rating Scale (C-SSRS)¹¹ will be used to assess suicide ideation, intent, plans, and behavior. C-SSRS interviews will be conducted by trained research staff supervised by [name] with consultation from Drs. [name] and [name]. Training procedures consist of: a) review of written materials, b) didactic instruction; c) practice interviews with review and feedback from senior staff; and 4) continued practice, training and feedback until high agreement with established consensus ratings are met

(e.g. 3 consecutive C-SSRS ratings are within 2 points of our consensus ratings). We will assess interviewers' reliability in an ongoing manner. Following initial training, interviewers and senior staff meet on a monthly basis to review tapes, address questions/issues, and monitor interrater reliability.

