Other Symptoms. We will use the following self-report scales: the Modified Scale for Suicide Ideation (MSSI)¹³ which provides a score indicating overall severity of suicide ideation; and the PROMIS-29, which assesses pain intensity on seven health domains (physical function, fatigue, pain interference, depressive symptoms, anxiety, ability to participate in social roles and activities, and sleep disturbance). We will also have participants in both study conditions complete the PROMIS Depression Short Form each week of the intervention to assess depressive symptoms. In addition, we also will assess the change in distress and perceived helpfulness during each week of the intervention for those assigned to LifePlans: 1) how distressed participants felt while watching the videos (5 point scale from "more distressed" to "less distressed"), 2) how distressed they felt after watching the videos (5 point scale from "more distressed" to "less distressed"), and 3) how helpful they felt the videos were (5 point scale from "very unhelpful" to "very helpful"). In order to ascertain inclusion criteria, we will use chart review and the Psychosis Screening Questionnaire³¹ to screen out people at baseline. Finally, we will use the self-blame subscale on the Personal Suicide Stigma Questionnaire (PSSQ) which is a self-report measure that has been found to be reliable and valid for assessing stigma in persons who have suicidal behaviors.

Potential Mediators. Potential mechanisms will be assessed using the following self-report scales: the Multidimensional Scale of Perceived Social Support (MSPSS)²¹, which is a reliable and valid measure of 3 aspects of social support (family, friends, and significant other); the Brief Cope²², which assesses strategies used for coping in response to negative life experiences ; and the Valuing Questionnaire (VQ) which is a reliable and valid measure that assesses the extent to which a person lives by their values.

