We will use several strategies to increase retention for assessments. Research staff will remind participants about appointments, maintain a list of locator contacts for each participant, reach out to contacts as needed, schedule assessments regardless of intervention participation, and have flexibility in when assessments are scheduled. Finally, we will provide transportation if needed for appointments.

Phase 3: Pilot RCT

The aim is to conduct a pilot RCT (n=40), with participants randomized to treatment as usual (TAU) or TAU + LifePlans. We will enroll hospitalized patients with a suicide plan/attempt prior to admission in the past month (see full inclusion criteria below). Methods will be similar to those described in the open trial (see previous section for Phase 2), with only the differences noted below. We will continue to focus on acceptability and feasibility, including an evaluation of the proposed research design.

Phase 3: Control condition description and rationale

The control condition will be TAU, which, as noted above, will include Hospital Safety and Discharge Planning as part of inpatient care, followed by outpatient care at a CNE outpatient site. In choosing TAU as a control condition, we considered the nature of the LifePlans intervention. LifePlans is designed to be adjunctive to TAU and in fact to encourage adherence to outpatient treatment plans developed in the hospital. We did not choose a more robust control condition because LifePlans is designed to be a lower-intensity intervention (thus increasing its potential reach) and not to replace existing treatments (but, in fact, to enhance them).

Phase 3: Randomization

Participants will be randomized using a 1:1 ratio to either TAU or TAU + LifePlans. Randomization will be stratified by: a) gender (male/ female/ non-binary) and b) suicide attempt vs. plan prior to admission. Treatment arm assignments will be blocked in blocks of 4 or 6 participants (randomly ordered). A staff member with no other study responsibilities will set up randomization tables in REDCap, and other research staff will not have access to the tables. Participants will be randomized following the baseline assessment using the randomize feature in REDCap. This ensures allocation concealment.

C3. Specific Procedures or Treatments

See C2. Study Design.

C4. Data Analysis

Date most recently revised 3/22/2022

Protocol Version 2.5

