1. *Current psychiatric hospitalization with recent (past month) suicide plan (with or without intent), or a suicide attempt within 48 hours prior to hospitalization*, as indicated on the hospital chart and confirmed by administration of the C-SSRS¹¹. Specifically, on the C-SSRS, this is operationalized to a "yes" on item 3, 4, OR 5, AND/OR a "yes" to suicide attempt/ interrupted attempt/ or aborted attempt.
2. *Ability to speak, read, and understand English well enough to complete the procedures of the study.*
3. *Aged 18 or older.*
4. *Regular access to a means of watching videos* (i.e., a smartphone, tablet, computer, or DVD player) *in the place they expect to live after discharge.*
5. *No current psychotic symptoms* (based on chart review and the Psychosis Screening Questionnaire)
6. *Plan to continue outpatient treatment.*

No minors, prisoners, fetuses/neonates, or decisionally/ cognitively impaired individuals will be recruited.

B. Recruitment and Consent Procedures

Phase 3: With a HIPAA waiver (see below) we will screen medical records at Butler Hospital to identify potentially eligible participants. Patients meeting inclusion criteria that can be assessed via chart review (i.e., criteria 1, 3, 5), and whose attending physician does not mark as ineligible for research, will be approached by research staff. Patients will be approached in-person on the units or if they are attending a partial hospital program virtually, they will be contacted by phone using the number provided in their chart. Staff will provide a description of the study and invite patients to participate in screening to determine study eligibility. Those consenting and meeting all inclusion criteria will be invited to participate in the study.

For the clinical stakeholder interview during Phase 2, we will consult with our investigator team to identify appropriate clinical stakeholders to approach about study participation. Once identified, Drs. [name] or [name] or another member of the research team will contact the stakeholder directly to introduce the study. If interested, the participant will be mailed or emailed (via REDCap link) a copy of the Stakeholders Informed Consent form in addition to a brief description of the video series. The participant will then be consented over the phone or via videoconferencing. The consent process will be documented either through audio or video recording or via electronic REDCap signature.

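### Does the attempt-versus-plan stratum, and the differing wording of the qualifying attempt, need a change to the protocol?

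*Combined protocol and SAP*

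**What the plan says.** Four places in the protocol bear on the point.

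- **Phase 3: Pilot RCT** summarises enrolment in one line: "We will enroll hospitalized patients with a suicide plan/attempt prior to admission in the past month (see full inclusion criteria below". Plan and attempt share one window here.
- **Section 3.A, criterion 1** gives the plan a past-month window, but the attempt must be "a suicide attempt within 48 hours prior to hospitalization". It is to be read from the chart and confirmed with the C-SSRS. The next sentence translates the criterion into C-SSRS answers: a yes on item 3, 4 or 5, and/or a yes "to suicide attempt/ interrupted attempt/ or aborted attempt". It states no look-back of its own.
- **Phase 3: Randomization** stratifies by gender (three levels) and by "suicide attempt vs. plan prior to admission", 1:1, in random blocks of 4 or 6. Participants are randomized in REDCap after the baseline assessment.
- **Assessments.** The Research Assessments table schedules the C-SSRS at baseline but does not give it the inclusion code. The Other Symptoms paragraph says "In order to ascertain inclusion criteria, we will use chart review and the Psychosis Screening Questionnaire", and does not mention the C-SSRS.

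Specific Aims describes the population as "hospitalized patients (including people enrolled in a partial hospital program) with a recent suicide attempt/plan".

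**The concern.** Attempt and plan are set against each other in the stratum, yet the and/or in the C-SSRS sentence expressly lets in patients with both. No section says which stratum they enter, how far back an attempt counts for the stratum, or whether an interrupted or aborted attempt counts as an attempt there.

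The entry rule also seems to be written three ways: past month in the overview, 48 hours in criterion 1, and no stated window in the C-SSRS sentence. The missing inclusion code and the silence of Other Symptoms seem to leave the instrument's role at entry unsettled. For partial-hospital patients, no section says which admission date starts the 48 hours if someone steps down from an inpatient stay.

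If staff read these places differently, enrolment would be inconsistent. The trial would also lose some of the balance on attempt status that stratification is meant to give, and Specific Aims names suicide behaviors among the outcomes to be compared between arms.

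**Working it through.** **1. Which text governs entry.** The overview points the reader to the full criteria, and section 3.A says participants must meet the criteria listed there. The overview is therefore a summary and criterion 1 is the rule. The C-SSRS sentence says how criterion 1 is operationalized, so it is part of that criterion. Read this way it keeps the criterion's windows and makes clear that interrupted and aborted attempts count.

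**2. Worked cases under that reading.**

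| Patient | Eligible? | Stratum |
|---|---|---|
| Attempt 10 days before admission, no plan | No; criterion 1 governs over the summary | Not applicable |
| Aborted or interrupted attempt within 48 hours, no plan | Yes; the C-SSRS sentence defines the criterion | Not stated whether it counts as an attempt |
| Past-month plan and attempt 10 days before admission | Yes, through the plan | Not stated |
| Past-month plan and attempt within 48 hours | Yes, by both routes | Not stated |

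Eligibility is settled in all four rows. Only the stratum label stays open, and only for eligible patients with both events or with an interrupted or aborted attempt.

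**3. Can the open label bias the comparison?** No. The stratum value is entered before REDCap returns the allocation, and both arms face the same ambiguity. Any convention applied consistently gives a valid stratum and blocked balance on that convention. Inconsistent coding can only weaken balance.

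**4. How much balance could be lost.** The protocol gives no stratum frequencies and no coding error rate, so this is illustrative.

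- From the protocol: n = 40, 1:1, blocks of 4 or 6, and 3 × 2 = 6 strata, hence 40/6 = 6.7 participants per stratum on average.
- Assumed: gender split 45/50/5, 30/60/10 or equal thirds; attempt share 30% or 50%; 0%, 10% or 20% of participants miscoded, either in both directions or from attempt to plan only.
- Quantity: the probability that the arms differ by 4 or more attempt patients, over 5,000–6,000 simulated trials per setting.

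| Setting | Probability of a difference of 4 or more |
|---|---|
| Stratified, no miscoding | 0.024–0.049 |
| Stratified, 10% of participants miscoded | 0.116–0.177 |
| Stratified, 20% of participants miscoded | 0.177–0.244 |
| Stratified on gender only | 0.220–0.296 |

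The mean signed difference is about 0 in every setting. The mean absolute difference rises from about 1.2–1.4 patients with no miscoding to about 1.8–2.1 at 10%, an increase of less than one patient.

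The assumed rates are severe. With a 30% attempt share and one-way errors, 10% of participants means 10/30, or one third, of attempt patients miscoded, and 20% means 20/30, or two thirds. At 2–5% of participants miscoded the probability is about 4–12%.

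**5. What the analysis does with the stratum.** C4. Data Analysis plans descriptive statistics, states that refining procedures is the primary aim, and cautions against using pilot effect sizes for power. No model uses the stratum as a covariate. Potential Moderators leaves moderator testing to future, larger studies.

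**6. The instrument coding.** Criterion 1 itself requires C-SSRS confirmation, and the table schedules the C-SSRS at baseline. The Other Symptoms sentence sits apart from the C-SSRS paragraph and goes on to speak of screening people out. The missing inclusion code is a clerical slip.

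**The case for a change.** The strongest case for a change rests on the stratum alone. It needs no contested reading of eligibility: the and/or admits patients with both events, the stratum treats the two as exclusive, and the pointer to the full criteria does not help because those criteria contain no stratum rule. If 20% of participants were coded inconsistently, most of the balance the stratum is meant to give would be lost (0.177–0.244, against 0.220–0.296 with no stratification on attempt). The remedy would cost a few words and one field definition. A pilot meant to refine procedures should also hand on a reproducible stratum to the larger trial.

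The omission stands: the both-events rule is not written down. The size does not. The miscoding rates are assumed, and they describe staff who share no convention. Whoever sets up the REDCap randomization tables and the field that feeds them has to settle what each value means. The C-SSRS interviewers are trained to consensus ratings and meet monthly on reliability; that training does not cover stratum coding as such, but it does make divergent reading of the underlying events less likely. The summary line is looser than criterion 1 but gives way to it by its own words. The step-down question for partial-hospital patients is hypothetical, since no section describes that pathway.

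**Conclusion.** No change to the plan is called for. The point comes down to a detail that staff settle when the REDCap stratum field is built, a loosely worded overview line, and a table code left out. No stated rule yields a wrong result, and the arm comparison is not biased. The worst effect is some loss of balance on attempt status in a 40-patient pilot whose planned analysis is descriptive: less than one patient in mean absolute imbalance if 10% of participants were miscoded, and none if one convention is kept.

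This rests on three readings or assumptions: that criterion 1 governs over the summary that defers to it; that the C-SSRS sentence carries that criterion's windows; and that study staff use one convention for patients with both events. The number of such patients is not documented, and the simulation inputs beyond the design itself are assumed. Which attempt window is clinically suitable is not judged here.
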